3.2 Study Procedures and Visit Structure

The study visit schedule and procedures are described in Table 1. The study includes a maximum of approximately 29 weeks of treatment with 1-month (4 weeks) and 4-months (16 weeks) Follow-up visits after the Efficacy Evaluation Visit (V13).

Table 1. Study Procedures and Visit Structure

	Screening Visits		Baseline Visit (Day 1)	Injections Visits ²									Efficacy Evaluation Visit ¹⁰	Follow-up Visits	
Visit	V1 ¹⁴ -30d	V2 ¹	V3 ¹	V4	V5	V6	V7	V8	V9	V10	V11	V12	V13 ¹⁴	V14	V15
Window (days)		±4h ⁵		±2d									±3d	±3d	±7d
Procedure	•													•	
Informed Consent	X														
Inclusion/Exclusion Criteria	X		X												
Demographics	X														
Medical and Surgical History	X		X												
Blood Draw for Safety Labs ¹⁴	X												X		
Urinalysis	X												X		
Pregnancy Test ³	X		X		X		X		X		X		X		
Vital Signs (includes weight and height at screening)	X		X	X	X	X	X	X	X	X	X	X	X		
Physical Examination	X												X		
Full Body Dermatologic Examination to identify the															
presence of any wart type			X				X						X		X
Presence or absence of common warts in designated			37				37						37		37
anatomical areas			X				X						X		X
Evaluation of presence or absence of common warts other			37										37	37	37
than the measured and mapped injectable common warts			X										X	X	X
Common warts measurement and mapping (up to 6															
injectable common warts including all primary injectable			X	X	X	X	X	X	X	X	X	X	X	X	X
warts)															
Evaluation of primary injected wart(s) status				X	X	X	X	X	X	X	X	X	X	X	X
Selection of primary injectable wart(s) ⁹		X													
Selection and Mapping of non-primary common wart(s)			X	v	v	X	X	X	Х	v	Х	X			
for injection ⁸			Λ	X	X	Λ	Λ	Λ	Λ	X	Λ	Λ			
DTH Challenge Injection (30-min observation period)	X^{13}														
DTH Evaluation		X													
Blood Draw for Biomarkers Evaluation	X^6				$X^{6,12}$								X^6		
Randomization			X												
Intralesional Injection (30-min observation period)			X	X	X	X	X	X	X	X	X	X			
Give Subject Diary	X^7		X	X	X	X	X	X	X	X	X	X			
Review/Retrieve Subject Diary		X^7		X	X	X	X	X	X	X	X	X	X		
Medical Photographs ⁴			X		X		X				X		X	X	X
Hypopigmentation and Scarring Assessments ¹¹			X	X	X	X	X	X	X	X	X	X	X	X	X
Concomitant Medications	X	X	X	X	X	X	X	X	X	X	X	X	X	X	X
Adverse Events	X	X	X	X	X	X	X	X	X	X	X	X	X	X	X

- 1. Screening Visit 2 and Baseline Visit may be performed on the same day if all screening information and data are available.
- 2. If the medical Investigator deems appropriate because of tolerance issues the injection schema may be changed to every 3 weeks instead of 2 weeks for a maximum of 10 doses.
- 3. Female of childbearing potential only. Serum pregnancy at screening and urine pregnancy test at other visits.
- 4. At selected sites, for a maximum of 10 subjects per cohort.
- 5. Post 48h of DTH injection from V1.
- 6. Cohort 1 only.
- 7. DTH Diary
- 8. Applicable only if there is complete resolution of the primary injected wart(s).
- 9. One for Cohort 1 and 2; and up to 4 in Cohort 3.
- 10. If complete resolution of all common warts, not just the primary injected wart(s), is observed at any of the visits following Baseline, the procedures described under Visit 13 will be performed. This visit also will be performed in the event of an early termination.
- 11. To be initially assessed at Visit 3 and prior to the first injection in case of selection and mapping of non-primary common wart(s) for injection (V4 to V12). To be re-assessed at the site of resolved primary and non-primary injected wart(s) must be recorded as an AE if at Baseline (V3), or prior to the first injection in case of selection and mapping of non-primary common wart(s) for injection (V4 to V12) it was assessed as absent.
- 12. Prior to injection.
- 13. On certain occasions, administering the DTH challenge at V1 may result in a difficulty scheduling V2 at the 48 hour time required (for example V1 on a Thursday or Friday resulting in V2 on a weekend). The investigator may perform the DTH challenge on an additional visit after V1 (subvisit) in order to schedule an acceptable V2, provided the DTH challenge is performed within 1 week of V1 and a urine pregnancy test is performed if required for a given subject. Urine pregnancy testing not required for women of non-childbearing potential defined as post-menopausal for at least 2 years or surgically sterile (tubal ligation, oophorectomy, or hysterectomy).
- 14. V1 and V13 should not be scheduled on a weekend if at all possible due to shipping restrictions of blood samples.

3.3 Randomization Schedule and Blinding Procedures

This is a double-blind study defined as blinding of subjects, investigators, and site personnel not involved in study medication preparation and accountability. A concealed, centralized randomization list generated by an unblinded Sponsor representative will be used to assign the cohort and treatment to the subjects using an internet-based system. Randomization will be unbalanced (3:1) in favor of Candin. To maintain the blind, a qualified, unblinded person at each study site will prepare the syringes containing the medication (CANDIN or saline) independently from the Investigator performing the injection and making the evaluations. Subjects will be randomly assigned to cohorts first, and then to treatment, according to Table 2.

Randomization Number of Number of Number of Ratio between Randomized Randomized Subjects in **Anatomical Regions Subjects** to Candin to Placebo **Cohorts within Cohorts** Stratum Cohort 1 = 3325 8 Single 66 1:1 Cohort 2 = 3325 8 Cohort 1 = 1914 5 5 Multiple 90 4:4:11 Cohort 2 = 1914 Cohort 3 = 52

Table 2. Randomization Structure by Stratum, Cohort, and Treatment

The first 16 subjects will be randomized (1:1) to Cohort 1 or 2 until medical assessment of the first eight subjects of Cohort 2 (6 on active and 2 on placebo) completing three injections supports continuation of the study to Cohort 3. Once medical assessment supported continuation of the study to Cohort 3, subsequent subjects with warts in at least 2 different anatomical regions will be randomized to Cohort 1, 2, or 3 in a ratio of 4:4:11 to ensure that the treatment assignment for the overall 156 subjects will approximately preserve the above randomization structure.

The treatment randomization assignments will be kept secured from the Investigator and/or blinded site staff in the unblinded pharmacy binder until the database is finalized and hard locked.

The investigational site will assign each subject a subject identifier number during screening that will be used on all subject documentation throughout the study. Numbers will be assigned in ascending order using Sponsor's numbering system.

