Cohort 2: Approximately fifty-two subjects will receive 0.5 mL of either Candin (n=39) or placebo (n=13) intralesionally in the largest (primary) common wart every second week $(14 \pm 2 \text{ days})$ for a maximum of 10 injections. The same procedures will be followed in the event of complete response or recurrence as described for Cohort 1.

Cohort 3: If the safety data from Cohort 2 support continuation of the study (defined as medical assessment of the first eight subjects of Cohort 2 completing three injections), approximately 52 subjects planned for Cohort 3 will receive either 0.3 mL/wart Candin (n=39) or placebo (n=13), with a total per visit not to exceed 1.2 mL. Subjects in Cohort 3 must have injectable common warts in at least 2 different anatomic regions. Candin or placebo will be injected under the largest (primary) wart per major anatomical region (left or right; arm, hand, leg, foot excluding sole, or the torso) for a minimum of two and a maximum of four injections per visit, every second week (14 ± 2 days) for a maximum of 10 visits with injections. No more than one wart per anatomical region will be injected on any given visit. If any primary injected wart exhibits a complete response, the next largest injectable common wart will be injected with the randomized study medication at the same dose (maximum of 4 injections per visit), providing the new injectable wart is not within the same anatomical region as other currently injected warts. (If an injected wart recurs after exhibiting a complete response, it will be reinjected instead of the non-primary injected wart that was injected at the previous visit.) This injection strategy will be repeated for a maximum total of 10 injection visits per subject or until all injectable common warts exhibit a complete response, if it occurs before the end of the 10 injection visits.

Two Follow-up visits are included in the study to further assess the efficacy and safety of the study medication. Follow-up information will be obtained for subjects who discontinue their participation in the study. All procedures scheduled for during Follow-up Visit 1 and Follow-up Visit 2 should be completed for early termination subjects, as well as for those subjects who have complete resolution of all common warts prior to their Efficacy Evaluation visit (V13).

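### The 4:4:11 ratio in SAP 3.3 yields Table 2's 19/19/52 only if all 90 multi-region subjects are allocated with it, but it starts after the first 16 subjects, so Cohort 3 is expected to fall short by an amount that depends on their mix

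*SAP*

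**What the plan says.** Table 2 in SAP 3.3 covers all 156 subjects. The single-region stratum has 66, split 1:1 into 33 and 33 for Cohorts 1 and 2. The multi-region stratum has 90, split 4:4:11 into 19, 19 and 52 for Cohorts 1, 2 and 3.

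The text below the table describes two phases. In the lead-in, "The first 16 subjects will be randomized (1:1) to Cohort 1 or 2 until medical assessment of the first eight subjects of Cohort 2" supports opening Cohort 3. Nothing limits these 16 to subjects with warts in a single region. After that review, later multi-region subjects are allocated among the three cohorts "in a ratio of 4:4:11 to ensure that the treatment assignment for the overall 156 subjects will approximately preserve the above randomization structure".

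SAP 3.1 and Protocol 6.1 plan Cohort 3 at about 52 subjects, 39 on Candin and 13 on placebo.

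**The concern.** The same ratio is used in two ways that do not fit together. In Table 2 it describes how the whole multi-region stratum ends up. In the text it is the allocation rule for only the part of the stratum that comes after the lead-in. Multi-region subjects enrolled in the lead-in go entirely to Cohorts 1 and 2. To finish at 19/19/52, the later subjects would have to be allocated more heavily to Cohort 3 than 4:4:11.

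At stake is the size of Cohort 3, the only arm in which several warts are injected per visit, and the match between the cohort sizes the SAP states and those its own rule is expected to produce.

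**Working it through.** **Inputs.** From SAP 3.3: 90 multi-region and 66 single-region subjects; ratio 4:4:11 (sum 19); lead-in of 16 subjects, 1:1 to Cohorts 1 and 2; Candin to placebo 3:1. From the protocol's sample size section: 24% resolution on placebo and 70% on active. From SAP 7.1.1: two-sided α = 0.05. Not in the documents: m, the number of multi-region subjects among the first 16. I take the planned mix, 16 × 90/156 = 9.2, as the central case and show the full range 0 to 16. I also assume that multi-region enrolment ends at 90.

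**Step 1: reproduce Table 2.** 90 × 4/19 = 18.9 and 90 × 11/19 = 52.1. This is 19/19/52, so the table treats all 90 as allocated at 4:4:11.

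**Step 2: add the lead-in.**

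- Cohort 3 = (90 − m) × 11/19
- Multi-region subjects in each of Cohorts 1 and 2 = m/2 + (90 − m) × 4/19
- Cohort 3 on Candin = 0.75 × Cohort 3

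| m | Cohort 3 | of which Candin | Cohorts 1 and 2, multi-region, each | Shortfall against 52 |
|---|---|---|---|---|
| 0 | 52.1 | 39.1 | 18.9 | none |
| 4 | 49.8 | 37.3 | 20.1 | 2.2 (4%) |
| 9.2 | 46.8 | 35.1 | 21.6 | 5.2 (10%) |
| 16 | 42.8 | 32.1 | 23.6 | 9.2 (18%) |

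With 33 single-region subjects in each of Cohorts 1 and 2, cohort totals at the planned mix are about 54.6, 54.6 and 46.8, against 52 each.

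**Step 3: could m be negligible?** If each of the first 16 is multi-region with probability 90/156, the chance of m ≤ 3 is about 0.2%, and the chance of m = 0 is about one in a million.

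**Step 4: what if Cohort 3 is simply filled to 52?** At 4:4:11 this needs 52 × 19/11 = 89.8 multi-region subjects after the review, or 99.0 in total at m = 9.2. With 156 overall, the strata become about 57/99 instead of 66/90. The multi-region cells of Cohorts 1 and 2 become 4.6 + 89.8 × 4/19 = 23.5 each instead of 19.

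**Step 5: effect on power.** Normal approximation, 24% vs 70%, no dropout, unstratified comparison of two proportions. The planned Cochran-Mantel-Haenszel test is stratified by single versus multiple regions (Protocol 14.5.1.1) and Cohort 3 lies wholly in the multiple stratum. I therefore show both the multi-region placebo (5 + 5 + 13 = 23) and the full placebo pool (39).

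| Candin in Cohort 3 | 23 controls | 39 controls |
|---|---|---|
| 39 | 96.1% | 99.1% |
| about 35 (m = 9.2) | 95.3% | 98.8% |
| about 32 (m = 16) | 94.5% | 98.4% |

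**Step 6: controls.** Placebo is one in four in every cohort. The 90 multi-region subjects therefore include about 90/4 = 22.5 on placebo however they are divided among cohorts.

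**The case against.** The strongest reply is that the SAP promises only approximate preservation, and that cohort sizes and the total are all stated as approximate. If stratum membership is left to chance, the number of multi-region subjects among the 140 after the lead-in varies enough to give Cohort 3 a standard deviation of about 3.4 (√(140 × 90/156 × 66/156) × 11/19). The expected gap of 5.2 is about 1.5 of these. This tempers the point but does not remove it: chance variation goes both ways, while this gap is built into the rule and always falls on Cohort 3.

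The shortfall also needs assumptions. No passage caps the strata, so Cohort 3 could reach 52 through extra multi-region enrolment. That stands, but Step 4 shows that other cells of Table 2 then move, so the structure is still not preserved. The central list may also close cells at the Table 2 numbers. The documents available here do not show this, and the protocol's own randomization table is not visible, so that gap cannot be held against the plan. If the list does work that way, the SAP text should say so.

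A reader might go further and infer that Cohort 3 will certainly be under-filled, or that the defect leaves it with fewer usable controls. The documents support neither. The first depends on m and on where enrolment stops. The second fails at Step 6: the loss is in Candin subjects. Nor are the extra multi-region Cohort 1 subjects wasted, because SAP 7.1 pools them with Cohort 3 for the 0.3 mL comparison. That pool, both treatments together, goes only from 71 (52 + 19) to about 68.4 (46.8 + 21.6).

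**Conclusion.** The inconsistency is real and minor. As written, 4:4:11 matches Table 2 only when none of the first 16 subjects is multi-region. Otherwise, with the stratum ending at 90, Cohort 3 is expected to fall short: by about 5 subjects (10%) at the planned mix, and by between 0 and 9 across the possible range. A lead-in that continued past 16 while the safety review was pending could widen the gap. The size is conditional on m and on the 90-subject limit; the mismatch between the calibration of the ratio and its starting point is not.

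The consequence for inference is small. At the protocol's assumed rates, Cohort 3 power falls by 0.3 to 0.8 points at the planned mix, and by 0.7 to 1.6 points in the extreme case. This is a matter of making the stated rule and the stated numbers agree, and does not threaten the trial's primary comparison.

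**What to change.** If the safety review is still ahead, replace the fixed ratio with a rule that fills the remaining Table 2 cells: 52 in Cohort 3, and in each of Cohorts 1 and 2, 19 minus the multi-region subjects already enrolled there. This is correct for any split of the first 16 that leaves those cells open. At the planned mix the remaining cells are about 14.4 : 14.4 : 52, close to 3:3:11, which gives 52.3 in Cohort 3 and 18.9 multi-region subjects in each of Cohorts 1 and 2. A fixed ratio should serve only as an illustration, because the right one depends on m. The cost is a change to the parameters of the randomization list.

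The SAP is dated February 2018 against a December 2016 protocol, so allocation may already be past that stage. In that case, restate Table 2 and the Cohort 3 figures of 52 (39 and 13) as the numbers the rule is expected to deliver given the actual first 16, and remove the statement that 4:4:11 ensures the structure. The cost is one corrected table, the matching Cohort 3 figures in SAP 3.1, and one sentence.

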4 STUDY ENDPOINTS

4.1 Primary Efficacy Endpoint

The primary efficacy endpoint is the number and proportion of subjects with the primary injected wart(s) completely resolved at any treatment or Follow-up visit.

[figure not shown]
In Cohort 1 and 2, the largest common wart located on hands, feet (excluding soles), limbs, and/or trunk will be selected as the primary injected wart. In Cohort 3, the largest common wart per anatomical region (left or right; arm, hand, leg, foot (excluding sole) or the torso) will be selected as the primary injected warts for a minimum of 2 and a maximum of 4 warts. In Cohort 3 subjects, injected warts must be in different anatomical regions. Warts in flat, plantar, facial, periungual, or genital or in a region of pre-existing inflammatory condition are excluded from injection.

4.2 Secondary Endpoints

Secondary endpoints include the following:

1. Assessment of safety and tolerability of Candin:

Incidences of DTH Challenge immediate reactions and immediate injection hypersensitivity/reactions after study treatment, and all other treatment-emergent adverse events.

4.4 Safety Endpoints

Safety and tolerability will be assessed by evaluating the treatment-emergent adverse events and, the clinical laboratory results, and vital signs.

5 ANALYSIS POPULATIONS

The following populations will be used for the summaries and analyses of the study data.

5.1 DTH Safety Population

The DTH Safety population consists of all subjects who signed the informed consent and received the DTH Test treatment at the Screening visit.

The DTH Safety population will be used to summarize the adverse events including reactions due to DTH challenge injection that occurred prior to the randomized study treatment if the subject received any randomized treatment. Note that this population may include subjects that never got randomized and received no study treatment.

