7.12 DTH Challenge

At Screening Visit 1 (V1), the DTH test will be done by administering a single intradermal injection of CANDIN (0.1mL) on the volar surface of the forearm or on the outer aspect of the upper arm, at least 2 cm away from any primary injectable wart(s). The skin should be cleansed with 70% alcohol before applying the skin test. The intradermal injection must be given as superficially as possible causing a distinct, sharply defined bleb. An unreliable reaction may result if the product is injected subcutaneously. The subject will

Nielsen- CFW-2D Page 35 of 54

be asked to remain in the clinic for 30 minutes after receiving the injection of CANDIN for the DTH test, to assess any immediate reactions. A DTH diary will be handed to the subject, in order to capture any delayed reactions, prior to Screening Visit 2 (V2).

The test should be read on V2 at $(48 \pm 4 \text{ hours post DTH challenge injection that occurred at V1})$ by visually inspecting the test site and palpating the indurated area. Measurements should be made across two diameters. The mean of the longest and midpoint orthogonal diameters of the indurated area should be reported as the DTH response.

The measured DTH response must be between ≥ 5 mm and ≤ 25 mm in diameter to be considered a valid reaction. Responses <5 mm or >25 mm would exclude the subject from the study.

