9.2 Adverse Events

An AE is any untoward medical occurrence in a subject administered a pharmaceutical product, without regard to the possibility of a causal relationship with this treatment. Lack of drug effect is not an AE in clinical trials because the purpose of the clinical trial is to establish drug effect.

Any documented pregnancy will be tracked and followed through outcome. While pregnancy itself is not considered an AE or an SAE, any pregnancy complications or elective termination of a pregnancy for medical reasons will be recorded as an AE and evaluated as a possible SAE.

Prior to enrollment, study site personnel will note the occurrence and nature of each subject's medical condition(s) in the appropriate section of the source document and eCRF. During the study, site personnel will again note any change in the pre-existing condition(s) and the occurrence and nature of any AEs.

CANDIN will be administered in accordance with the US labeled indication for assessment of the subject's DTH response to Candida antigen. AE collection will begin at the time of the DTH injection (Screening Visit 1).

CANDIN administered intralesionally is the investigational product in this study. Treatment-Emergent AEs (TEAEs) will be those arising after the first intralesional wart(s) injection.

If a subject experiences an AE after the informed consent document is signed, but before CANDIN is Nielsen- CFW-2D Page 38 of 54

Protocol Final version 5.0: 06Dec2016

administered for assessment of the DTH response, the event will be recorded as a non-treatment emergent AE in the source document. If the subject is randomized, the non-treatment emergent event will also be captured in the eCRF. If the subject screen fails, the event will not be captured in the eCRF or in the clinical database.

AEs reported as related to CANDIN administered for assessment of the DTH response will be described in the source document and assessed for expectedness and regulatory reportability using the Candin package insert. If the subject is randomized, the AE related to Candin for the DTH assessment will also be captured in the eCRF.

Injection site AEs may be captured from either subject diaries or during Treatment and Follow-up Visits. In all cases, causality and severity of injection site TEAEs are assessed by Investigator as described in Sections 9.2.1 and 9.2.2, respectively.

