9.3 Serious Adverse Events

If a subject experiences a SAE after the informed consent document is signed, but before CANDIN is administered for assessment of the DTH response, the event will be recorded as a non-treatment emergent SAE in the source document. If the subject is randomized, the non-treatment emergent SAE will also be captured in the source and reported in the CRF. If the subject screen fails, the SAE will not be reported in

Nielsen- CFW-2D Page 40 of 54

^{**}Induration/Swelling should be evaluated and graded using the functional scale as well as the actual measurement.

the eCRF.

CANDIN will be administered in accordance with the US labeled indication for assessment of the subject's DTH response to Candida antigen. SAEs reported as related to Candin administered for the DTH assessment will be described in the source document and assessed for expectedness and regulatory reportability using the Candin package insert. If the subject is randomized, the SAE related to Candin administered for the DTH assessment will also be captured in the eCRF.

All SAEs occurring following wart injections and up to 30 days following the last wart injection will be captured in the source document and reported in the CRF.

A SAE (event/experience) or reaction is any untoward medical occurrence that at any dose:

- results in death,
- is life-threatening,

NOTE: The term "life-threatening" in the definition of "serious" refers to an event in which the subject was at risk of death at the time of the event; it does not refer to an event which hypothetically might have caused death if it were more severe.

- requires in-subject hospitalization or prolongation of existing hospitalization,
- results in persistent or significant disability/incapacity, or
- is a congenital anomaly/birth defect.

Medical and scientific judgment should be exercised in deciding whether expedited reporting is appropriate in other situations, such as important medical events that may not be immediately life-threatening or result in death or hospitalization but may jeopardize the subject or may require intervention to prevent one of the other outcomes listed in the definition above. These should also usually be considered serious.

Examples of such events are intensive treatment in an emergency room or at home for allergic bronchospasm; blood dyscrasias or convulsions that do not result in hospitalization; or development of drug dependency or drug abuse.

9.3.1 SAE Reporting:

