7.3.1 Adverse Events

TEAEs are defined as those occurring during or after the first wart injection of randomized study medication, or existing prior to the time of and worsening after the time of the first study dose, through final Follow-up Visit (V15) or Early Termination/Withdrawal. AEs with onset date prior to the first administration of randomized study medication will be classified as pretreatment AEs.

All AEs are to be coded with Medical Dictionary for Regulatory Activities (MedDRATM) version 17.0.

The frequency (event counts) and incidence (number and percent of subjects) of TEAEs, serious TEAEs, TEAEs leading to withdrawal, TEAEs by severity (most severe grading from

the same preferred terms within the same subjects), and TEAEs by causality (Related versus Not Related), frequent TEAEs (incidence \geq 5% in any treatment groups) will be summarized.

Injection site TEAEs, defined by any preferred terms containing the phrase of "injection site", will be summarized further.

DTH-related AEs that occurred during the DTH Screening time period (e.g., prior to the receiving the randomized study medication) will be summarized separately for DTH Safety population.

All further details collected for AEs will be presented in a listing.

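### The DTH Safety population counts screen failures in the denominator, but the protocol provides for eCRF entry of their DTH-related events only if they are randomized, so the tabulated incidence can only be too low

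*SAP*

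**What the plan says.** **Endpoint.** SAP 4.2 places the skin-test reactions in its secondary safety endpoint: "Incidences of DTH Challenge immediate reactions and immediate injection hypersensitivity/reactions after study treatment". Protocol 3.2 does not name DTH reactions among its secondary endpoints.

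**Denominator.** SAP 5.1: "The DTH Safety population consists of all subjects who signed the informed consent and received the DTH Test treatment at the Screening visit". It then states: "Note that this population may include subjects that never got randomized and received no study treatment". SAP 7.3.1 gives this population a separate summary of "DTH-related AEs that occurred during the DTH Screening time period".

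**Which events the population is for.** SAP 5.1 says it will serve to summarize adverse events, including reactions to the DTH injection, "that occurred prior to the randomized study treatment if the subject received any randomized treatment".

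**Data capture.** Protocol 9.2 starts AE collection at the DTH injection and puts DTH-related AEs in the source document. It continues: "If the subject is randomized, the AE related to Candin for the DTH assessment will also be captured in the eCRF". Protocol 9.3 has the matching sentence for serious events: "If the subject is randomized, the SAE related to Candin administered for the DTH assessment will also be captured in the eCRF". Later in Protocol 9.2, eCRF entry of all AEs and SAEs is promised for subjects randomized to study drug.

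**Link between the test and randomization.** Protocol 7.12, on the reading at 48 ± 4 hours: "Responses <5 mm or >25 mm would exclude the subject from the study".

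**The concern.** An incidence needs its numerator and denominator to cover the same people. Here the SAP sets the denominator as everyone exposed to the skin test, while the protocol's capture rule supplies events only from those who go on to be randomized. A DTH-tested subject who is not randomized would be counted as event-free whatever happened after the injection.

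The SAP appears to have created this population in order to report DTH safety in all exposed subjects. If the table is built as written, events that were not entered will read as events that did not occur, and the skin test will look better tolerated than it was.

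**Working it through.** The plan states no DTH reaction rate, number screened or screen-failure share, so there is no figure to reproduce. The check is an identity, followed by an illustration on assumed values.

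**Inputs**
- NR, number randomized: about 156 (Protocol 5).
- NS, number DTH-tested but not randomized: not given. Assumed through a share f = NS/(NR + NS) of 10%, 30% or 50%.
- pR and pS, proportions with a DTH-related event among randomized and non-randomized subjects: not given; assumed.
- Capture: events from R are in the database, events from S are not (Protocol 9.2 and 9.3 as written).

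**Formulas**
- Recorded incidence = pR·NR / (NR + NS)
- True incidence = (pR·NR + pS·NS) / (NR + NS)
- Recorded minus true = −pS·NS / (NR + NS)

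The difference is never positive. It is negative as soon as one non-randomized subject has a DTH-related event. If pR = pS, recorded/true = 1 − f, whatever the event rate and whatever NR.

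**One row in full**, f = 30%: NR + NS = 156/0.7 = 222.9, so NS = 66.9. With pR = pS = 10%, recorded = 15.6/222.9 = 7.0% and true = (15.6 + 6.7)/222.9 = 10.0%. The difference is −3.0 percentage points and the ratio is 0.70.

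| f (assumed) | Tested | Not randomized | pR | pS | Recorded | True | Recorded/true |
|---|---|---|---|---|---|---|---|
| 10% | 173 | 17 | 10% | 10% | 9.0% | 10.0% | 0.90 |
| 30% | 223 | 67 | 10% | 10% | 7.0% | 10.0% | 0.70 |
| 30% | 223 | 67 | 10% | 5% | 7.0% | 8.5% | 0.82 |
| 30% | 223 | 67 | 10% | 30% | 7.0% | 16.0% | 0.44 |
| 50% | 312 | 156 | 20% | 20% | 10.0% | 20.0% | 0.50 |

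The third and fourth rows show that the shortfall shrinks if screen failures react less and grows if they react more. The sign does not change.

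**The ambiguous clause in SAP 5.1.** The condition about having received randomized treatment can be read in two ways.
- As a time cut-off (for treated subjects, count only events before the first dose), it calls for screen failures' events, which the protocol does not route to the eCRF.
- As a limit on whose events count, the SAP itself sets a treated-only numerator over an all-tested denominator.

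The mismatch is present under both.

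**Effect of restricting the denominator.** With randomized subjects only, the result is pR. The dilution is gone, but the figure describes only subjects who passed screening, including the 5 to 25 mm criterion.

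**The case against.** **The protocol does not literally say that only randomized subjects' DTH events are entered.** Its explicit statement that a screen failure's event stays out of the eCRF and clinical database is written for events before the DTH injection. AE collection begins at that injection, the flow charts mark AEs at V1 and V2, and data capture is delegated to a Data Management Plan that is not public. The SAP is also later than the protocol (February 2018 against December 2016) and expects non-randomized subjects in this population. This stands as a limit on certainty: unseen data-management documents might capture more. But the conditional sentences in Protocol 9.2 and 9.3 naturally mean entry only on randomization, the later sentence in 9.2 points the same way, and nothing visible provides an alternative. If another route exists, the protocol wording should say so.

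**A reader might infer that the table loses the strongest reactors.** The documents do not support this for the endpoint named in SAP 4.2. That endpoint concerns immediate reactions, for which Protocol 7.12 sets a 30-minute observation period. The exclusion above 25 mm concerns induration at about 48 hours. The same rule removes responses below 5 mm, and nothing shows which group is larger or that either has a different rate of immediate reactions.

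**A reader might also put a rate of about 33% on the immediate reactions** by adding the 20% and 13% in Protocol 1.3. Both are given there as upper limits, so the sum is not an expected rate. The ratio 1 − f does not need it.

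**The reach is narrow.** This is correct. DTH testing is labelled use and precedes randomization. DTH-related events in all tested subjects are in source documents and are assessed for reportability (Protocol 9.2, 9.3 and 14.5.2.1).

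**Conclusion.** Wrong as written. SAP 5.1 and 7.3.1 pair an all-tested denominator with events that Protocol 9.2 and 9.3 enter on condition of randomization. Under that capture rule the DTH reaction incidence is too low by pS·NS/(NR + NS).

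The direction follows from the text, provided the conditional sentences carry their natural meaning and no unseen document captures more. The size cannot be derived from the documents: the ratios of 0.9, 0.7 and 0.5 rest on assumed screen-failure shares of 10%, 30% and 50% and on equal event rates in the two groups.

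The consequence is confined to the descriptive DTH safety table. Efficacy analyses, comparisons of treatment-emergent events (which start at the first wart injection) and reportability review are unaffected.

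**What to change.** **Preferred.** Amend Protocol 9.2 and 9.3 so that DTH-related AEs and SAEs are entered in the database for every subject given the DTH injection, randomized or not. The cost is one short eCRF form for DTH-tested screen failures; the information is already in the source documents.

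**If that is no longer possible.** In SAP 5.1, restrict the denominator of this summary to randomized subjects. Label the table as excluding subjects screened out, including those with a DTH response below 5 mm or above 25 mm. List non-randomized subjects' DTH reactions separately from source. The cost is about one sentence in the SAP and one listing.

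**In either case.** Reword the SAP 5.1 clause on receipt of randomized treatment so that it is plainly a time cut-off for treated subjects and not a rule on whose events count.
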